7. POSSIBLE ADVERSE EFFECTS AND CLASSIFICATION OF SEVERITY

① Infection

		Minor Adverse Effects	Severe Adverse Effects
Infec	ction	Viral infections without severe symptoms Bacterial infections treatable with oral antibiotics	Viral infections with severe symptoms Bacterial infections curable with intravenous antibacterial administrations

② Allergy/immunity (allergic effects/hypersensitivity)

• • • • • • • • • • • • • • • • • • • •		
	Minor Adverse Effects	Severe Adverse Effects
Skin symptoms	Localized urticaria Pruritus	Widespread rash Oculomucocutaneous syndrome Toxic epidermal necrosis Stevens-Johnson syndrome
Systemic symptoms	Angioedema (except pharyngeal edema)	Hypersensitivity syndrome Anaphylaxis Pharyngeal edema

3 Cardiovascular system

•	Minor Adverse Effects	Severe Adverse Effects
Hypotension	Asymptomatic hypotension	Symptomatic hypotension
Hypertension	Asymptomatic hypertension	Symptomatic hypertension
Arrhythmia	Supraventricular extrasystole Ventricular extrasystole (single) First-degree atrioventricular block	Supraventricular tachycardia Ventricular extrasystole (couplet or more) Ventricular tachycardia Second- or third-degree atrioventricular block Ventricular fibrillation Torsades de pointes, Cardiac arrest
Impairment of cardiac function	Ejection fraction of left ventricle (on echocardiogram) ≤60%	Ejection fraction of left ventricle (on echocardiogram) ≤40%
Thromboembolism		Deep vein thrombosis, Arterial thrombosis

4 Blood

	Minor Adverse Effects	Severe Adverse Effects
Anemia	20-25% hematocrit	<20% hematocrit
White blood cell count	3000-4000/mm ³	<3000/mm ³
Neutrophil count	1000-2000/mm ³	<1000/mm ³
Platelet count	50,000-100,000/mm ³	<50,000/mm ³
Bleeding	Subcutaneous hemorrhage	Mucosal hemorrhage, Intraorgan hemorrhage

Skin

	Minor Adverse Effects	Severe Adverse Effects
Ecchymosis	Localized	Generalized
Rash	Limited erythema or papules with no related symptoms	Generalized erythroderma Erythema or papules with itching or other symptoms

6 Digestive organs

	Minor Adverse Effects	Severe Adverse Effects
Ulceration	Erosion	Gastric ulcer Duodenal ulcer Hemorrhagic ulcer Perforation of digestive tract
Pancreatitis	Asymptomatic increase in pancreatic enzyme levels	Increase in pancreatic enzyme levels with related symptoms Pancreatic necrosis Hemorrhagic pancreatitis
Enteritis	Frequent bowel movements, Sometimes bloodstained with occasional rectal discomfort	Diarrhea requiring major transfusions Hemorrhagic enteritis
Melena	Positive fecal occult blood testing	Melena accompanied by shock or drop in hemoglobin requiring blood transfusions
Hematemesis	Transfusion not required	Transfusion required
Vomiting	Additional 2 to 5 times as compared with pretreatment average (per 24 hours)	Additional 6 or more times as compared with pretreatment average (per 24 hours)

$\ensuremath{\mathfrak{T}} \text{Liver}$

	Minor Adverse Effects	Severe Adverse Effects
Total bilirubin	3.0-9.9 mg/dl	≥10.0 mg/dl
AST, ALT (because these values rise in response to Kawasaki vasculitis, patients should be carefully monitored for increases)	100-499 IU/I	≥500 IU/I
Clinical symptoms, etc.		Jaundice Hepatomegaly Hepatic failure accompanied by bleeding tendency or mental confusion

® Endocrine system/metabolism

	Minor Adverse Effects	Severe Adverse Effects
Hyperglycemia	Asymptomatic hyperglycemia	Symptomatic hyperglycemia
Hypoglycemia	Asymptomatic hypoglycemia	Symptomatic hypoglycemia
Hypercholesteremia	Total cholesterol 220- 399 mg/dl	Total cholesterol ≥400mg/dl

9 Bleeding

	Minor Adverse Effects	Severe Adverse Effects
Nasal hemorrhage	Blood transfusion not required	Blood transfusion required
Subcutaneous hemorrhage	Scattered petechiae	Petechiae all over body
Intracranial hemorrhage		Hemorrhage visible on CT or MRI. Intracranial hemorrhage with symptoms

${\small 1\!0\!0} \ {\small Musculoskeletal} \ {\small system}$

	Minor Adverse Effects	Severe Adverse Effects
Arthritis	Mild discomfort accompanying joint Inflammation or swelling with no impairment in normal functioning	Pain (moderate to severe) accompanying joint Inflammation or swelling with normal functioning impaired
Muscular weakness	Asymptomatic Discovered only by medical examination	Related symptoms impair normal functioning
Osteonecrosis	Asymptomatic Visible only on imaging	Related symptoms impair normal functioning

11) Neurological disorders

	Minor Adverse Effects	Severe Adverse Effects
Aseptic meningitis	Accompanied only by mild headache and/or vomiting	Cerebrospinal fluid testing reveals increased cerebrospinal fluid cell count, Accompanied by severe clinical symptoms

$\ensuremath{\textcircled{12}}$ Eyes and vision

	Minor Adverse Effects	Severe Adverse Effects
Glaucoma	Increased ocular pressure without visual impairment	Increased ocular pressure accompanied by retinal changes Vision impaired
Cataracts	No clinical symptoms	Clinical symptoms such as visual impairment
Visual disorders	Minor, with no functional impairment	Impairs normal functioning

13 Pain

	Minor Adverse Effects	Severe Adverse Effects
Abdominal or joint pain, head or muscle aches	Mild discomfort with no functional impairment	Analgesics required Normal functioning impaired

(4) Respiratory disorders

	Minor Adverse Effects	Severe Adverse Effects
Cough	General (non-narcotic) antitussive relieves cough	Narcotic antitussive required to relieve cough
Apnea	Oxygenation required	Mechanical ventilation required
Dyspnea, Hypoxemia	Oxygenation required	Dyspnea on exertion and at rest Mechanical ventilation required
Pneumonia	Resolves with standard treatment	Mechanical ventilation required

(15) Renal and urinary disorders

	Minor Adverse Effects	Severe Adverse Effects
Hematuria	Microscopic hematuria only	Gross hematuria Blood transfusion required
Albuminuria	2+ or lower (qualitative analysis)	3+ or higher (qualitative analysis)
Micturition pain	Mild symptoms, no intervention required	Prominent symptoms requiring treatment
Renal failure	_	Dialysis required

16 Others

	Minor Adverse Effects	Severe Adverse Effects
Low body temperature	34.0-35.0°C (axillar)	<34.0°C (axillar)

8. CATEGORIES EVALUATED AND THE SCHEDULE FOR CLINICAL TESTING AND EVALUATION

8.1. Categories evaluated before patient registration

1)Patient background

Age in months, sex, height, weight, date at enrollment, past history of KD

2)Blood testing

Blood count: white blood cell count, % neutrophils, hematocrit, platelet count Biochemical tests: total bilirubin, AST, ALT, LDH, sodium, potassium chloride, BUN, Cr, total protein, albumin, blood glucose, total cholesterol, HDL cholesterol Immune serum: CRP, IgG, BNP

3) Urine testing (may be ignored if not collected)

Urine characteristics (sugar, albumin, occult blood), urine sediment

4) Echocardiography

Diameter of coronary artery, left ventricular ejection fraction, presence or absence of valvular disease, presence or absence of pericardial effusion

8.2. Testing and evaluation during study period

- 1) Laboratory testing: the recommended schedule for laboratory testing is as follows.
 - 2 days after enrollment (1 to 3 days after enrollment is allowed)
 - 1 week after enrollment (6 to 9 days after enrollment is allowed)
 - 2 weeks after enrolment (12 to 16 days after enrollment is allowed)
 - 4 weeks after enrollment (24 to 32 days after enrollment is allowed) Laboratory testing should be performed 2 to 3 times per week until serum CRP level decreases to ≤ 0.5 mg/dl.
- 2) Urine testing: as decided by attending physician
- 3) Echocardiography: the recommended schedule for echocardiography (all echocardiography exams must be digitally recorded)
 - 1 week after enrollment (6 to 9 days after enrollment is allowed)
 - 2 weeks after enrolment (12 to 16 days after enrollment is allowed)
 - 4 weeks after enrollment (24 to 32 days after enrollment is allowed)
- 4) Adverse events: Daily during the study period.

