2.3.2. Endpoints

Primary

• Incidence of CAA during the study period

Secondary

- Incidence of CAA at Week 4 after enrollment
- Z scores²²⁾ for right coronary artery and left main coronary trunk and anterior descending artery
- Incidence of need for additional rescue therapy
- Days of fever after enrollment
- Serum levels of CRP at Weeks 1 and 2 after enrollment
- Incidence of severe adverse events

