2.3.3. Clinical hypotheses and reason for number of registrants

The principal hypothesis of the present study is that patients with severe KD who receive the study treatment (IVIG with PSL) will have a significantly lower incidence of CAA during the study period as compared with the group receiving standard treatment (IVIG). If this does indeed prove to be true, then initial treatment with IVIG plus PSL will be judged to be more effective.

The target enrollment was set using data obtained from 1123 consecutive KD patients from August 2000 to August 2007 at 13 hospitals in Gunma and Saitama prefectures, Japan. ²³⁾ Eight KD patients who presented with CAA at admission and 109 KD patients with missing values were excluded from this study. Thus, data from 1006 KD patients (IVIG group n=896, IVIG+PSL group n=110) were analyzed. Of the 110 patients in the IVIG+PSL group, 90 were participants of a previously reported randomized trial. ¹⁸⁾ The other 20 patients were given IVIG+PSL according to the attending doctor's recommendations, except for 1 patient

whose parents desired treatment with IVIG+PSL. The table below shows clinical and coronary outcomes in the high-risk group.

	IVIG (n=298)	IVIG+PSL (n=48)
Nonresponse to treatment	51.7	20.8
Incidence of coronary artery abnormality during 1 month	18.1	6.3
Incidence of coronary artery abnormality at 1 month	8.4	4.2

The primary endpoint of the RAISE Study is to assess whether the incidence of CAA in the study treatment is significantly lower than that of the standard treatment during the study period. Based on the above data, the required sample size was calculated with the assumption that IVIG plus PSL would reduce the fraction of patients with CAA during the study period from 18% to 8%. With a 2-sided test, an α level of 0.05, and a power of 80% and assuming that 10% of the patients would not complete the study, a total sample of 392 patients would be required. Analyses were intent-to-treat. Fisher's exact test was used to test the null hypothesis, i.e. that the incidence of CAA would be equal between the 2 treatment groups during the study period.

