6.2. Random assignment and assignment adjustment factors

Dynamic random assignment of patients to their respective groups will be done using the minimization method at a 1:1 ratio. The adjustment factors include sex, age, and institution, classified by method of additional rescue therapy (Group A; IVIG retreatment only, Group B; IVIG retreatment and/or conventional dose of PSL, Group C; IVIG retreatment and/or pulsed dose methylprednisolone with or without subsequent PSL, Group D; IVIG retreatment and/or conventional dose of PSL and/or pulsed dose methylprednisolone with or without subsequent PSL and/or infliximab).

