12. STATISTICS

12.1. Principal analyses and criterion

The main goal of the present study is to determine whether, as compared with standard IVIG treatment, treatment with IVIG plus PSL results in a significant reduction in the primary endpoint, i.e. the incidence of CAA during the study period. To test the null hypothesis (namely, that the incidence of such complications will be the same in both groups), Fisher's exact test will be used to compare all applicable cases in the 2 groups. Because it is possible that the trial treatment could result in worse outcomes than standard treatment, all testing will be 2-sided. The significance level for all tests will be 5% (2-sided).

If statistical analysis reveals that the incidence of CAA during the study period is significantly lower in the trial treatment group than in the standard treatment group, the conclusion will be that the trial treatment with IVIG plus PSL is the more effective treatment. If no such significant decrease is found, the conclusion will be that treatment with IVIG remains the standard treatment for KD.

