12.2. Target number of subjects/ registration period/ follow-up periods

As mentioned in the background of the study (section 2.3.3., "Clinical hypotheses and reason for number of registrants"), the rate of CAA in the IVIG group is expected to be the same as in previous studies of this treatment, ie, approximately 18%. The study design has been established to determine whether the trial treatment (IVIG plus PSL) can achieve at least an additional 10% absolute reduction in the incidence of CAA during the study period, i.e. reduce the incidence rate to 8% or less. If the study requires a 3-year registration period and a 1-month follow-up period, and α is equal to 5% (2-sided) with a statistical power of 80%, the number of cases required for each group will be 176, for a total of 352 in the 2 groups. If a 10% drop-out rate is assumed, the final enrollment numbers are as follows.

Target number of subjects: 196 per group, for a total of 392 patients.

Registration period: 3 years. Follow-up period: 1 month after enrollment.

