12.4.2. Analysis of secondary endpoints related to efficacy

The secondary endpoints related to treatment efficacy include incidence of CAA at week 4 after enrollment, Z scores for the right coronary artery and left main coronary trunk and anterior descending artery, days of fever after enrollment, incidence of need for additional rescue therapy, and serum levels of CRP at Weeks 1 and 2 after enrollment. These secondary endpoints will only be analyzed during the interim analysis and at the end of the study, and only as secondary endpoints; there will be no correction for the multiplicity of tests when these endpoints are analyzed.

It is expected that the incidence of CAA at week 4 after enrollment will be lower in the IVIG plus PSL group than in the IVIG group, as this result is expected to be correlated with the largest diameter attained during the enlargement of the coronary artery, while these treatments are being administered.

As for incidence of need for additional rescue therapy, this can be considered to reflect the effectiveness of the treatments. It is therefore expected that this incidence will be lower in the IVIG plus PSL group than in the IVIG group.

As for days of fever after enrollment and serum levels of CRP at Weeks 1 and 2 after enrollment, these can be considered endpoints that depend on the suppression of KD vasculitis achieved by the treatments. It is therefore expected that, as compared with standard IVIG treatment, the period required for days of fever after enrollment will be shorter, and that serum levels of CRP at Weeks 1 and 2 after enrollment will be lower, in the IVIG plus PSL group.

Fisher's exact test will be used to evaluate the incidence of CAA at Week 4 after enrollment

and the incidence of need for additional rescue therapy; the interval estimation will be done with exact confidence intervals based on the binomial distribution.

Z scores for the right coronary artery and left main coronary trunk and anterior descending artery, days of fever after enrollment, and serum levels of CRP at Weeks 1 and 2 after enrollment will first be tested for normality with the Kolmogorov-Smirnov test. Variables that are found to have a normal distribution will be compared using the unpaired t-test; those with a non-normal distribution will be compared using the Mann-Whitney U-test.

12.5. Termination of the study if the incidence of giant coronary aneurisms in the trial treatment group is high

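### Laboratory test frequency follows CRP, so severe adverse events defined by a laboratory value alone may be looked for more often in the IVIG arm

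*Protocol*

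**What the plan says.** Protocol Section 8.2 recommends laboratory tests in four windows after enrollment in both arms: days 1–3, 6–9, 12–16 and 24–32. It then adds: "Laboratory testing should be performed 2 to 3 times per week until serum CRP level decreases to ≤ 0.5 mg/dl". It does not say which analytes the added draws must include.

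Section 12.4.2 states the expectation that "serum levels of CRP at Weeks 1 and 2 after enrollment will be lower, in the IVIG plus PSL group".

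Section 2.3.2 lists "Incidence of severe adverse events" as a secondary endpoint, and Section 12.4.1 treats adverse event incidence as the safety endpoint. In Section 7 several rows become severe on a number alone. An example is "White blood cell count", which is severe below 3000/mm³. The others are neutrophils below 1000/mm³, platelets below 50,000/mm³, hematocrit below 20%, total bilirubin of 10 mg/dl or more, AST or ALT of 500 IU/l or more, and total cholesterol of 400 mg/dl or more.

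**The concern.** An event that exists only as a blood result can be found only when blood is taken. If one arm is tested for longer, it has more chances to cross a cut-off at the same underlying risk. Here the stopping rule for testing is itself a response to treatment, and the protocol predicts which arm will respond better. The expected direction is more laboratory-only severe events recorded on IVIG alone, which would make PSL look relatively safer on that component.

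A detail in Section 5.1.1 adds to this. The 15-day PSL taper starts at the same CRP value that ends the extra testing. During the taper, laboratory events in the PSL arm are therefore sought only at whatever common windows remain.

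At stake is the laboratory-only part of one secondary endpoint. The primary endpoint and the sample size are untouched.

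**Working it through.** **Is there a figure to reproduce?** No. The protocol gives no number of tests per patient, no time to CRP normalization and no rate of laboratory-only severe events. The sizes below rest on stated assumptions.

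**Inputs from the protocol.** Four common windows, with nominal days 2, 7, 14 and 28 (Section 8.2). Extra draws 2 to 3 times a week until CRP is at or below 0.5 mg/dl (Section 8.2). Target of 196 patients per group (Section 12.2), used only to turn percentages into patients.

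**Assumptions.** CRP normalizes about one week later on IVIG alone. Each draw covers the relevant analytes. Each draw has the same independent probability q of showing a severe value in both arms.

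**Number of draws.** Place twice-weekly draws on days 2, 5, 9, 12, 16 and so on, and stop at the first draw on or after normalization.
- Normalization on day 7: draws on days 2, 5, 7, 9, 14 and 28, which is 6.
- Normalization on day 14: draws on days 2, 5, 7, 9, 12, 14, 16 and 28, which is 8.

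On a three-times-weekly calendar the same contrast is 5 against 7 draws, again a gap of two, because the Week 2 visit coincides with one of the extra draws. Simply adding 2 to 3 tests to 6 gives 8 to 9, so 9 is an upper figure for one extra week.

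**Detected incidence with k draws:** 1 − (1 − q)^k.

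| q per draw | k = 6 | k = 8 | k = 9 | Difference, points |
|---|---|---|---|---|
| 0.5% | 2.96% | 3.93% | 4.41% | 1.0 to 1.4 |
| 1% | 5.85% | 7.73% | 8.65% | 1.9 to 2.8 |
| 2% | 11.42% | 14.92% | 16.63% | 3.5 to 5.2 |

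For q = 1%: 1 − 0.99^6 = 0.0585, 1 − 0.99^8 = 0.0773 and 1 − 0.99^9 = 0.0865. The gaps of 0.0187 and 0.0280, times 196, are about 4 and 5 patients.

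**Sensitivity to normalization time, q = 1%.**
- Day 7 in both arms: equal draws, ratio 1.00, no bias.
- Day 14 on IVIG against day 10 on PSL: 8 against 7 draws (ratio 1.14) or 7 against 7 (ratio 1.00), depending on the calendar.
- Day 14 against day 7: ratio 1.3 to 1.4.
- Day 21 against day 7: 10 against 6 draws or 10 against 5, that is 9.6% against 5.9% or 4.9%, ratio 1.6 to 2.0. This needs CRP to stay raised two weeks longer on IVIG alone.

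Positive correlation between tests in one patient shrinks all these differences. An abnormality that lasts long enough to be seen at a common visit adds nothing to the gap.

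**The case against.** A reader might infer that the schedule hides the harm of the steroid. The protocol does not support that. The corticosteroid effects listed in the rescue-therapy table of Section 5.2.1 are return of fever on dose reduction, infection, hypertension, thrombosis and electrolyte imbalance. None is a laboratory-only severe event in Section 7: severe infection is defined by symptoms or treatment, severe hypertension must be symptomatic, thrombosis is clinical, and electrolyte imbalance has no row. Severe hyperglycemia must also be symptomatic, and ulcer is not a blood-test finding. Section 8.2 records adverse events daily in both arms, so the number of draws does not govern these events.

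The premise is also partly inferred. Section 12.4.2 predicts lower CRP at Weeks 1 and 2, not a later time to 0.5 mg/dl. The nonresponse figures in Section 2.3.3 (51.7% against 20.8%) rest on fever as defined in Section 3.4, so they do not measure how long testing lasts. The full panel is itemized only for pre-registration testing in Section 8.1, so the extra draws may be mainly CRP.

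These points stand, and they limit the concern to laboratory-only events and to a possible bias.

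Two further objections carry less weight. The first is that secondary endpoints are exploratory and that Section 12.4 warns against reading a non-significant result as no difference. That moderates the conclusion but does not make ascertainment equal. The second is that counting rules belong in a statistical analysis plan. The source of the problem, however, is the testing rule written in Section 8.2, not a missing detail.

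**Conclusion.** The concern holds as a risk of unequal ascertainment, confined to severe adverse events set by a laboratory value alone. The expected direction favors PSL. With one extra week of raised CRP on IVIG alone, the full panel at each draw and an equal, independent 1% risk per test, the spurious difference is about 1.9 to 2.8 points, or 4 to 5 patients per 196. With 0.5% to 2% per test it runs from about 1.0 to 5.2 points. Within-patient correlation lowers these figures. They fall to zero if CRP normalizes at the same time in both arms or if the extra draws measure CRP only. None of the per-test risks or normalization times comes from the protocol. Clinically defined severe events are unaffected, and the protocol does not show that steroid harm would in fact be concealed.

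**What to change.** Leave the testing schedule in Section 8.2 and the all-event comparison of severe adverse events as they are. In Section 12.4.1 add two items:

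1. A between-arm comparison of laboratory-only severe events restricted to the four common windows of Section 8.2 (days 1–3, 6–9, 12–16 and 24–32). Use one test per window, the one nearest the nominal day.
2. The number of laboratory tests per patient, by arm. Counting by analyte would also show whether the extra draws covered more than CRP.

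The cost is wording and a little more analysis, with no new tests and no change to care. The restricted comparison misses transient events between windows. Those events stay in the all-event comparison and in safety reporting, which is why it should be added beside the all-event comparison and not replace it.

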9. ETHICAL CONSIDERATIONS

9.1. Patient protection

All researchers involved in the present study shall carefully abide by the Helsinki Declaration while conducting this research.

9.2. Informed consent

9.2.1. Explanation given to patients and their families

Before patients are registered, the attending physician will give a copy of an explanatory document (approved by the facility's IRB) to the patient and/or their family member(s) and verbally explain the details of the procedures to them.

9.2.2. Consent

After the above explanation is given and the patient and/or their family member(s) confirm that they clearly understand the procedures involved, they will be asked if they wish to participate in the study. If the patient or their family member(s) consent to participate in the study, the physician who explained the procedures, together with the patient and/or their family member(s) who consented to participate in the study, will write their names, the patient's name, and the date consent is given on the attached consent form (or other official consent form approved by the facility). Then, both the physician and patient and/or their family member(s) will sign the form.

